Hypotheses: During saline/glycerol (control) infusions, patients with CPT2, VLCAD, and LCHAD/TFP deficiency will have similar ectopic lipid stores, and similar (or better) Rd and lower fasting Ra compared to control subjects and patients with MCAD deficiency. In contrast, during the intralipid infusion ectopic lipids will increase in the FAO patients and controls alike, but insulin sensitivity will worsen (decreased Rd) in controls and patients with MCAD deficiency, but not in those with CPT2, VLCAD, or LCHAD/TFP deficiency.

B. Specific Aim 2: To determine the effect of distinct FAO disorders on tissue-specific lipid metabolism and insulin resistance compared to matched controls. We will measure blood, skeletal muscle, and adipose levels of lipids, intermediates of FAO (including organic acids) and amino acids by metabolomics profiling, and adipose and muscle insulin signaling in FAO patients and matched controls participating in aim 1.

Hypotheses: In parallel with our hypothesized outcomes in Aim 1, we expect that CPT2, VLCAD, and LCHAD/TFP-deficient patients, despite intracellular accumulation of lipids and long-chain FAO intermediates in muscle and adipose tissue, will be “protected” from intralipid-induced insulin resistance by exhibiting greater insulin signaling pathway activation and glucose and FFA uptake than tissue from controls. On the other hand, accompanying the accumulation of medium chain FAO intermediates, subjects with MCAD deficiency will have reduced fat and muscle insulin action (similar to controls).

C. SIGNIFICANCE

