Type 2 diabetes (T2DM) affects over 18 million Americans, but the pathogenesis of insulin resistance underlying T2DM remains incompletely understood,(14, 19, 47, 48, 93, 101) and novel therapeutics are still needed. The proposed studies in this application will advance our understanding of the cellular basis for insulin resistance and potentially resolve a major controversy in this field: i.e., whether impaired insulin signaling results from defective mitochondrial function and subsequent accumulation of cytosolic lipid and byproducts of FAO (for review, see ref (62) and below) or from increased flux through the FAO cycle and subsequent generation of metabolic intermediates (for review, see ref (69) and below). In addition to providing a unique opportunity to better understand the interface between FFA metabolism and the expression of insulin resistance in humans, the results of these studies will also help inform the on-going development of potential pharmaceutical targets for the treatment of insulin resistance and T2DM (for review see refs (86, 104)).

D. INNOVATION

Previous investigators have studied the interactions of lipid and glucose metabolism in patients with existing insulin resistance or a familial predisposition for diabetes. While these studies have yielded important new insights into the importance of mitochondrial dysfunction in insulin resistance, we will recruit and study a novel group of patients with inherited FAO defects. By taking advantage of our current clinical trials program in patients with FAO disorders, autosomal-recessive genetic disorders that severely limit specific enzymatic steps in the FAO cascade, these studies will allow us to pinpoint a specific level of mitochondrial FAO dysfunction that results in either induction of, or protection from, insulin resistance under conditions of high-fat exposure characteristic of developed societies consuming Western diets and exhibiting high rates of obesity. These studies will, therefore, have relevance well beyond the rare patient with a FAO disorder and indeed, by using advanced metabolomics and muscle and adipose tissue analyses to assess tissue-specific metabolite signatures associated with cellular lipid accumulation, impaired insulin signaling, and FAO products, will allow for identification of potentially novel mechanistic candidates of insulin resistance that would not otherwise be possible.

E. APPROACH

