Metabolomics: Plasma, muscle, and subcutaneous adipose tissue aliquots will be extracted, derivatized, centrifuged, decanted and dried as previously described.⁴² A set of 13 C8-C30 fatty acid methyl ester internal standards will be added, samples derivatized, and analytes separated using an Agilent 6890 gas chromatograph (Santa Clara, CA). Chromatography will be performed followed by mass spectrometry by a Leco Pegasus IV time-of-flight mass spectrometer (St. Joseph, MI) with 280°C transfer line temperature, electron ionization at 270eV and an ion source temperature of 250°C. Mass spectra will be acquired from m/z 85–500 at 17 spectra s21 and 1850 V detector voltage. Result files will be exported to our servers and further processed by the metabolomics BinBase database. All database entries in BinBase will be matched against the Fiehn mass spectral library of 1,200 authentic metabolite spectra. Identified metabolites will be reported if present within at least 50% of the samples per study design group. Peak heights of quantifier ions defined for each metabolite in BinBase will be normalized to the sum intensities of all known metabolites and used for statistical investigation. Compiled data sets will be analyzed using an appropriate array of multivariate data analyses techniques including principal components analysis, hierarchical cluster analyses, and projection to latent structures discriminant analyses using the an R-based Microsoft Excel Add-in developed in the laboratory of [name] and SIMPCA-P v.12.0.

Laboratory analysis of Tissue Biopsies: Subcutaneous WAT and muscle biopsies will be processed for explant assays of glucose and FFA uptake as well as for the preparation of lysates for Western immunoblot

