The primary analyses to compare disease groups with healthy controls will use mixed models with a random effect for matched pair to allow for correlation between the observations on the matched observations. In addition to the random pair effect, a disease effect (disease versus healthy), and a diagnostic group effect (CPT2, VLCAD, LCHAD/TFP, MCAD), we will also incorporate a fixed effect for the order of testing (interlipid infusion tested first or second). The hypotheses focus on the comparisons between diseased individuals and their matched controls with regard to the difference in outcomes under the two conditions (glycerol vs interlipid infusion). For these analyses, we will use the difference in a given outcome (e.g., Rd uptake) between infusion conditions as the dependent variable and compare these differences between diseased and matched controls, separately for the four diagnostic groups (CPT2, VLCAD, LCHAD/TFP, MCAD). Although we will conduct a formal test of interaction of disease (disease vs healthy) and diagnostic group, we are not powered for such a test and, hence, will focus on separate inferences for the four disease groups. Note that, as indicated in the hypotheses, we expect to find differences between the controls and the CPT2, VLCAD, and LCHAD/TFP subjects, but not between the controls and the MCAD subjects. For the latter comparison, our emphasis will be on estimating the magnitude of the mean differences via 95% confidence intervals rather than formal hypothesis testing. We will use a significance level of 0.05 for each outcome comparison, with no adjustment for multiple comparisons due to the limited sample sizes. We are unable to increase sample sizes due to the small study populations and budgetary constraints, so cannot power the study to take into account the multiple comparisons. However, we will present for each outcome, both unadjusted p-values as well as p-values adjusted for the two multiple comparisons (one for each disease group) using the Holm procedure.(38)

Power Considerations:

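### Nothing in the plan controls false positives across metabolites: the only error-rate rule is 0.05 per outcome, and the metabolomics methods carry no validation or selection threshold

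*Combined protocol and SAP*

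**What the plan says.** Section V, Statistical Analysis, gives one error-rate rule: "We will use a significance level of 0.05 for each outcome comparison", "with no adjustment for multiple comparisons due to the limited sample sizes". It also promises "p-values adjusted for the two multiple comparisons (one for each disease group) using the Holm procedure", separately for each outcome. The rule is framed generally: "we will use the difference in a given outcome (e.g., Rd uptake) between infusion conditions as the dependent variable". The MCAD comparison is to rest on confidence intervals more than on tests.

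Metabolite levels are Aim 2 measurements: "We will measure blood, skeletal muscle, and adipose levels of lipids, intermediates of FAO (including organic acids) and amino acids by metabolomics profiling". Under Laboratory Methods, Metabolomics, three sample types are processed ("Plasma, muscle, and subcutaneous adipose tissue aliquots will be extracted") and spectra are matched to a "library of 1,200 authentic metabolite spectra". A metabolite is reported if it is found in at least half of the samples in each group. Normalised peak heights then go forward to statistical work, for which the paragraph names PCA, hierarchical clustering and PLS-DA.

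The anticipated results for Aim 2 predict group differences in long-, medium- and short-chain acylcarnitines, ketones and amino acids. The Innovation section says that the metabolomics and tissue analyses "will allow for identification of potentially novel mechanistic candidates of insulin resistance". No section gives a rule for calling a metabolite a candidate, and false discovery rate is not mentioned.

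**The concern.** Testing a few named clamp outcomes at an unadjusted 0.05 is defensible in a rare disease, and the plan gives its reason openly. That reason does not carry over to a screen of many metabolites in three sample types and several diagnoses, whose stated use is to suggest new mechanisms. There the number of tests, not the size of the trial, determines how many false leads appear.

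The Holm step does not help, because the number of metabolites never enters it. PLS-DA does not help either: with 8 patients per diagnosis and many more variables than subjects, it can separate groups on noise unless it is validated. At stake is the credibility of any metabolite reported as a candidate. The clamp and MRS conclusions are not affected.

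**Working it through.** **The plan's own figures.** The documents state no expected number of false metabolite findings. They do state power at an unadjusted 0.05 with n = 10, which shows the level the design was built on. Inputs are the SDs and hypothesised changes in Table 5 (Power Considerations).

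- SD of within-subject change = √(s₁² + s₂² − 2·r_w·s₁·s₂). SE of the patient–control difference = SD·√(2(1 − r_b)/n). Power is from a two-sided paired t test with n − 1 df.
- PDK4, correlations 0: SD = √(0.06² + 0.38²) = 0.385; difference 0.62 − 0.18 = 0.44; power 62.6% (stated 63%).
- PDK4, correlations 0.25: SD = 0.370; power 78.1% (stated 78%).
- GIR, correlations 0: SD = √(9.3² + 7.8²) = 12.14; difference 31.5 − 5.7 = 25.8; power 98.8% (stated about 97%).

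The PDK4 figures reproduce and GIR is within two points. At the 8 per diagnosis given under Study Population, PDK4 power at zero correlation is 50.5%.

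**Expected false positives if metabolites are tested singly.** Let m be the number of metabolites tested. The documents do not give m, so the values below are assumptions; 1,200 is only the library size. With 3 sample types and the 3 long-chain groups, and no true effects:

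expected false positives = m × 3 × 3 × 0.05 = 0.45·m

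| m (assumed) | one sample type, one group (0.05·m) | 3 sample types × 3 groups (0.45·m) |
|---|---|---|
| 50 | 2.5 | 22.5 |
| 100 | 5 | 45 |
| 200 | 10 | 90 |
| 400 | 20 | 180 |
| 1,200 | 60 | 540 |

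To reach 24 expected false positives takes m = 24/0.45, about 54, over all nine combinations; 24/0.15 = 160 over three; and 24/0.05 = 480 in one. For 100 independent nulls, the chance of at least one false positive is 1 − 0.95¹⁰⁰ = 99.4%. Correlation between metabolites leaves the expected count unchanged but widens its spread. In a simulation with m = 200, no true effects and correlations of about 0.3 in size, the central 90% of counts ran from 57 to 133.

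**What the planned Holm step leaves.** Simulated Holm adjustment within one outcome leaves about 0.05 expected false findings per metabolite per sample type, whether 2, 3 or 4 groups are compared. Over 3 sample types that is about 15 for m = 100 and 30 for m = 200.

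**What share of hits would be false.** This depends on how many effects are real, which the documents do not say.

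- Assume each real effect has the 50.5% power found above. With 5% of effects real, the false share is 0.95 × 0.05 / (0.95 × 0.05 + 0.05 × 0.505) = 0.0475/0.0728 = 65%. With 10% real it is 0.045/(0.045 + 0.0505) = 47%.
- In a simulation with m = 200 (1,800 tests), 8 pairs, 10% real effects of 1.5 SD and the same correlation, unadjusted 0.05 gave about 82 false and 171 true hits, so 82/253 = 32% were false.

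**Effect of selecting on q.** In that simulation, Benjamini-Hochberg at q = 0.05 over all 1,800 tests left about 4 false and 80 true hits. With no real effects, about 92 false hits fell to about 0.1.

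**The case against.** The strongest reply is that the 0.05 rule was never meant for the metabolomics data. It stands in the paragraph on the primary analyses, its example outcome is Rd, and power is given only for GIR and PDK4. The Metabolomics paragraph has its own analysis sentence, which lists multivariate methods and no test of a single metabolite. The Innovation section speaks only of potentially novel candidates and sets no declaration rule.

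Most of this stands. A reader might infer that the plan commits to testing every metabolite at 0.05; the documents do not say so. But the general rule excludes nothing, and the Aim 2 predictions concern particular metabolites and classes, so single-metabolite comparisons are foreseeable. If candidates come only from PLS-DA instead, no cross-validation, permutation test or cut-off is stated. On either reading, the error rate of a declared candidate is uncontrolled.

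A reader might also count all four diagnoses and arrive at 100 × 3 × 4 × 0.05 = 60, or 120 for 200 metabolites. The plan puts MCAD mainly to estimation, so three groups are the fair basis.

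**Conclusion.** The point holds as a gap: no rule limits false positives across metabolites, and no rule says how a candidate is chosen. If metabolites are tested singly under the stated rule, 45 to 90 false positives are expected for an assumed 100 to 200 metabolites over three sample types and three long-chain groups, or 5 to 10 within one sample type and group. These figures assume that no effect is real. The plan itself predicts marked acylcarnitine differences, so the true count would be lower.

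Two stronger conclusions may tempt a reader. One is that dozens of false candidates are certain. The documents support neither the metabolite count nor the testing scheme that this needs. The other is that most hits would be noise. The false share was 32%, 47% or 65% under three sets of assumptions, and the documents do not allow a choice among them.

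**What to change.** 1. Leave the rules for the clamp and MRS outcomes as they are.
2. List the acylcarnitine, ketone and amino-acid hypotheses from the Aim 2 anticipated results as a separate pre-specified family, with its metabolites or class sums, its contrasts and its own error rule. Predicted effects then do not pay for the wide screen.
3. Label the remaining metabolomics work exploratory. State whether metabolites will be tested singly, in which sample types and contrasts, and report how many were tested.
4. Report Benjamini-Hochberg q-values within each sample type and contrast beside the raw p-values. Call a metabolite a candidate only on q, at a threshold (for example 0.10) fixed before the year-4 batch analysis. Printing q-values without selecting on them would remove no false hits.
5. Support any selection based on PLS-DA with cross-validation or a permutation test that respects the matched pairs.

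The cost is SAP wording, one output column and a validation run. The real downside is fewer declared metabolites, including some true ones. In the simulated example, true hits fell from about 171 to 80 while false hits fell from about 82 to 4. That example used q = 0.05 over all tests together, so the figures for q = 0.10 within each sample type and contrast will differ. The Timeline places the metabolomics batch run in year 4, after the clamps, so the rule can be fixed before those data exist.

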For each outcome, we have two measurements on every subject, one for each infusion condition. Our analyses will focus on comparisons between patients and controls of the *differences between outcomes* under the two conditions. We expect to see meaningful differences between controls CPT2, LCHAD/TFP, and VLCAD-deficient participants. These are the groups of interest for power calculations, whereas for MCAD, our aim is to provide useful descriptive information. There are two sets of correlations

between measures that need to be considered in power calculations (and statistical analyses). The first is the correlation between outcome measures on a given subject under the two infusion conditions, the second is the correlation of the differences in outcomes under the two infusion conditions, between each subject and his/her matched pair. For power calculations, we considered various values for each of these two correlations and used standard deviation estimates for each infusion condition as reported for glucose infusion rate (GIR) and for PDK4 mRNA levels (81, 94). GIR is a primary result during the HEC, closely related to insulin resistance (specific aim 1). PDK4 message is associated with our hypothesized mechanisms for insulin resistance in muscle and adipose tissue (Specific Aim 2). Mean and SD values for these outcomes in healthy controls are given in **Table 5**. We assume that normal controls and MCAD subjects will have mean outcomes as given in the table but that subjects with CPT2, VLCAD, and LCHAD/TFP disorder will have mean decreases when given the interlipid infusion that are less than 10% from that under the glycerol infusion condition for GIR and a mean increase of less than 100% for PDK4 mRNA. That is, we expect the mean change from glycerol infusion condition to be less than 5.7, and 0.18 for GIR, and PDK4 mRNA, respectively, for the CPT2, VLCAD, and LCHAD/TFP subjects.

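### The Holm adjustment is set for two comparisons, but the plan formally targets three disease groups and compares four with controls

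*Combined protocol and SAP*

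**What the plan says.** All the relevant text is in Section V.

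- **Comparisons.** The dependent variable is the difference in an outcome between the two infusions. Patients are compared with matched controls within each of CPT2, VLCAD, LCHAD/TFP and MCAD. Because the interaction test is underpowered, the authors "will focus on separate inferences for the four disease groups".
- **MCAD.** No difference from controls is expected there, and the emphasis is on "estimating the magnitude of the mean differences via 95% confidence intervals rather than formal hypothesis testing". Power Considerations agrees: "We expect to see meaningful differences between controls CPT2, LCHAD/TFP, and VLCAD-deficient participants", "whereas for MCAD, our aim is to provide useful descriptive information".
- **Main inference.** The plan uses a "significance level of 0.05 for each outcome comparison, with no adjustment for multiple comparisons", and gives small populations and budget as the reason.
- **Supplementary inference.** For each outcome it will also present "p-values adjusted for the two multiple comparisons (one for each disease group) using the Holm procedure".

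**The concern.** Holm's procedure needs one input besides the p-values: the number of hypotheses in the family. The plan gives that number as two and, in the same phrase, defines the family as one comparison per disease group. With four groups compared and three formally targeted, the definition gives three or four.

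An analyst who follows the number would multiply the smallest p-value by 2 and leave the rest unchanged. That under-adjusts. A reader of the adjusted column could then believe that a single-group result survives correction when it does not. Even an analyst who follows the definition must still choose between three and four, and the text does not settle this before results are seen.

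**Working it through.** **Reproducing the count.** Section V lists four patient-versus-control comparisons per outcome. Taking MCAD out as estimation leaves 4 − 1 = 3. Neither count is two.

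Other sources for a count of two:

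- The two infusions are not the source, because the dependent variable is already the difference between them.
- Two outcomes are not the source, because the adjustment is made for each outcome.
- Pooled long-chain patients plus MCAD would give two families, but Section V says the four groups are analysed separately. Pooling would also make MCAD one of two formal tests, against its stated role.
- VLCAD and LCHAD/TFP alone would give two, and the last column of Table 5 names only these. But CPT2 is in the hypotheses, the enrolment (8 per group, four groups), the analysis text and the power text.

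**Effect on reported p-values.** With ordered values p(1) ≤ p(2) ≤ …, the Holm-adjusted value is the running maximum of (m − i + 1) × p(i). The multipliers are 3, 2, 1 for m = 3 and 4, 3, 2, 1 for m = 4. The literal rule is taken as 2, 1, 1(, 1). The p-values below are illustrative.

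| Unadjusted | Literal two | Correct Holm |
|---|---|---|
| 0.02, 0.03, 0.04 | 0.04, 0.04, 0.04 | 0.06, 0.06, 0.06 |
| 0.001, 0.03, 0.04 | 0.002, 0.03, 0.04 | 0.003, 0.06, 0.06 |
| 0.02, 0.03, 0.04, 0.50 | 0.04, 0.04, 0.04, 0.50 | 0.08, 0.09, 0.09, 0.50 |

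The choice between three and four can also matter. A smallest p-value of 0.015 becomes 2 × 0.015 = 0.030, 3 × 0.015 = 0.045 or 4 × 0.015 = 0.060.

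**Family-wise error per outcome at a nominal 5%, independent tests.**

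- No group differs. The literal rule errs when the smallest p-value is at most 0.05/2 = 0.025.
  - Three tests: 1 − 0.975³ = 0.0731.
  - Four tests: 1 − 0.975⁴ = 0.0963.
  - Under any dependence the bounds are 3 × 0.025 = 0.075 and 4 × 0.025 = 0.10.
- One group differs and is detected. The remaining nulls are then tested at 0.05 each.
  - Three tests: 1 − 0.95² = 0.0975.
  - Four tests: 1 − 0.95³ = 0.1426.
  - Correct Holm: 1 − (1 − 0.05/2)² = 0.0494 and 1 − (1 − 0.05/3)³ = 0.0492.
- For reference, three wholly unadjusted tests with no true difference give 1 − 0.95³ = 0.1426.

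**Simulation check.** In 400,000 simulated sets of independent tests, the literal rule gave 0.0735, 0.0970, 0.0975 and 0.1427 for these four cases, in the order listed. Correct Holm gave 0.0492, 0.0494, 0.0490 and 0.0496. With a residual variance shared across groups (assumed 27 degrees of freedom, from 32 pairs), the literal rule gave 0.0709, 0.0938, 0.0968 and 0.1397, and correct Holm stayed between 0.0479 and 0.0489.

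**The case against.** The best defence is that the sentence names Holm's procedure and defines the family. A competent analyst would count the p-values and ignore the stray number, and multipliers of 2, 1, 1 over three tests are not Holm at all. This stands as far as it goes: every inflated figure above applies only if the number governs. It does not make the number right, and it leaves three versus four open.

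Second, if all three long-chain effects are real, as the plan expects, nothing is inflated. A three-test family then contains no true null. In a four-test family only MCAD can be falsely rejected, with probability at most 5% under either rule. This is correct. Inflation needs at least two true nulls in the family. But a multiplicity adjustment is there for the case where the expected effects are not all present.

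Third, the main inference is unadjusted by design, the power figures are stated at level 0.05 and do not use the count, and a reader who sees the unadjusted values can recompute Holm. All true, and this limits the weight of the point.

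Fourth, the text gives MCAD an emphasis on estimation but does not exclude an MCAD test, so four is a defensible count. That is fair, and the fix allows for it.

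**Conclusion.** The concern holds: a count of two matches no family that the current text defines. It may be left over from a design with two long-chain groups, which would fit Table 5 and the 20 long-chain subjects in Table 6 (two groups of 10), but that is inference.

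The consequence is limited to the supplementary adjusted column. Applied literally, the smallest adjusted p-value is two thirds of its correct value with three tests and half with four. Family-wise error runs from about 7% to 14% in the cases computed, instead of 5% or less. These rates assume near-independent tests, at least two true nulls, and literal use of the number. Not every adjusted value changes, since the largest p-value can carry a multiplier of 1 under any count. No planned conclusion changes. The sentence should still be corrected, because it is a wrong number in a stated analysis rule.

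**What to change.** In Section V, replace two with three and name the family: CPT2, VLCAD and LCHAD/TFP, each against its matched controls, for each outcome. State that MCAD lies outside the family and is reported as an estimate with a 95% confidence interval. If an MCAD p-value will be reported, include it and set the count to four. Settle this before results are seen.

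The cost is one sentence and somewhat larger adjusted p-values. Design, sample size, data collection and the unadjusted main inference are unaffected.

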To address these controversies, we will study a unique population of patients with inherited defects in one of four mitochondrial enzymes in the FAO pathway: 1) carnitine palmitoyltransferase 2 (CPT2); 2) very long-chain acyl-CoA dehydrogenase (VLCAD); 3) trifunctional protein (TFP, which includes long-chain 3-hydroxyacyl-CoA dehydrogenase (LCHAD)); and 4) medium-chain acyl-CoA dehydrogenase (MCAD). These proteins are required for the oxidation of sequentially shorter fatty acids (long-chain and medium-chain), respectively. We will use these patients to formally test the hypothesis that *intrinsic defects in mitochondrial function involving oxidation of long-chain, but not medium-chain, fatty acids are sufficient to prevent intralipid-induced insulin resistance.*

In a randomized, crossover study design, patients and a healthy control group will receive infusions of either intralipids or a control solution during hyperinsulinemic-euglycemic clamps. Glucose appearance (primarily due to hepatic glucose production) and glucose disposal (primarily by muscle tissue) will be measured, as will intrahepatic and intramyocellular lipid content (ectopic fat) by magnetic resonance spectroscopy, metabolite accumulation in muscle and fat using advanced metabolomics methodology, and insulin signaling pathway component expression and activation in the same biopsy samples.

In the first studies to test the relationships between impaired FAO, accumulation of intracellular lipid and lipid oxidation intermediates, and insulin resistance in humans, we propose the following specific aims:

A. Specific Aim 1: To measure the effect of intralipid infusions on ectopic fat and systemic glucose metabolism in FAO patients and matched controls. We will measure ectopic lipid deposition in muscle and liver by ¹H magnetic resonance spectroscopy (MRS) as well as glucose appearance (Ra) in the fasting state and insulin-mediated glucose disposal (Rd) during hyperinsulinemic-euglycemic clamps and co-infusion of either intralipids or saline/glycerol in patients with a FAO disorder and matched controls.

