In **Table 6**, we show the differences between groups in mean change that can be detected with 80% power at level 0.05 when the sample size per long-chain disorders is 20. For n=10 subjects, we have adequate power for detecting expected differences for GIR and PDK4 mRNA with modest correlation between repeated observations on the same subject and between matched pairs. For GIR, even with zero correlation, we would have about 97% power at level 0.05 to detect the expected difference in change between groups (31.5 vs 5.7) with n=10. For PDK4 mRNA, we could detect the expected difference in change (-0.62 vs -0.18) with 63% power if zero correlation and with 78% power if the correlation is 0.25 between and within n=10 matched patients.

Table 5: Glucose Infusion Rate (GIR), and PDK4 mRNA/actin in healthy controls and hypothesized mean differences in subjects.				
Outcome	Glycerol Infusion	Interlipid Infusion	H_a : mean Δ In Controls and MCAD	H_a : mean Δ In VLCAD and LCHAD/TFP
GIR ($\mu\text{mol}/\text{kg}/\text{min}$) (n=9)	57.2 ± 9.3	25.7 ± 7.8	31.5	5.7
PDK4 (mRNA/actin) (n=10)	0.18 ± 0.06	0.8 ± 0.38	-0.62	-0.18

Data are mean \pm standard deviation from Roden et al and Tsintzas et al. GIR = glucose infusion rate; PDK4 = pyruvate dehydrogenase kinase 4; H_a : mean Δ = hypothesized mean difference.

Table 6: Change between glycerol infusion and interlipid infusion that can be detected between control and the VLCAD, LCHAD/TFP and CPT2 groups with 80% power at level 0.05 with n=20 subjects long-chain FAO disorders.				
Outcome	Mean Δ (Glycerol – Intralipid) Controls	Correlation between observations on the same subjects	Correlation of Δ between matched controls and patients	Mean Detectable Δ (Glycerol – Intralipid)* LCHAD/TFP subjects
GIR	31.5	.25	.25	17.6
	31.5	.50	.25	20.0
	31.5	.50	.50	22.1
PDK4 mRNA	0.62	.25	.25	0.17
	0.62	.50	.25	0.19
	0.62	.50	.50	0.27

Δ = change; * Note that changes smaller than these can be detected with greater power as smaller changes are further from the changes expected in the control groups.

Timeline: Enrollment and clamp procedures will be completed in years 1, 2, and 3. Biopsy assays and insulin signaling measures will be completed real time with collection of the muscle and adipose samples during years 1-3. In year 4, we will batch analyze stored plasma, muscle, and adipose samples for metabolomics to control for run variation of the metabolomics methods, prepare manuscripts and present the results of the project.

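### No Aim 1 outcome is designated primary: the hypothesis and model example use Rd, the only Aim 1 power is for GIR, and each outcome comparison is tested at an unadjusted 0.05

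*Combined protocol and SAP*

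**What the plan says.** - **Specific Aim 1** lists lipid content by spectroscopy together with "glucose appearance (Ra) in the fasting state and insulin-mediated glucose disposal (Rd) during hyperinsulinemic-euglycemic clamps". GIR is not listed.
- **Specific Aim 1, Hypotheses:** during the lipid infusion, "insulin sensitivity will worsen (decreased Rd) in controls and patients with MCAD deficiency, but not in those with CPT2, VLCAD, or LCHAD/TFP deficiency".
- **III. Study Design, clamp procedure:** the quantities to be calculated from the tracer data are Rd and basal Ra.
- **V. Statistical Analysis:** "we will use the difference in a given outcome (e.g., Rd uptake) between infusion conditions as the dependent variable". Rd is the only example given. On error control: "We will use a significance level of 0.05 for each outcome comparison, with no adjustment for multiple comparisons due to the limited sample sizes". The reason offered is that sample size is fixed by small populations and budget, "so cannot power the study to take into account the multiple comparisons". Holm-adjusted p-values will be shown beside the unadjusted ones for each outcome, for two comparisons described as one per disease group.
- **Power Considerations:** "GIR is a primary result during the HEC, closely related to insulin resistance (specific aim 1". Then: "For GIR, even with zero correlation, we would have about 97% power at level 0.05", for a change of 31.5 against 5.7 with n=10. PDK4 mRNA is the only other outcome powered. Rd is not.
- **The term primary outcome** appears once, under Study Design, to say that the abdominal MRI measures are not one.

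**The concern.** Aim 1 asks whether long-chain patients are protected from lipid-induced insulin resistance. The plan does not say which measurement answers that question. Rd carries the hypothesis, GIR carries the power, and the signalling and explant measurements are predicted to move the same way. Each gets its own 0.05 test in each of three long-chain groups. If Rd is not significant in a group but GIR or a tissue measure is, the plan has no rule for what to conclude.

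GIR and Rd are related but not interchangeable. At steady state, GIR equals Rd minus residual endogenous glucose production. The plan itself uses a tracer because the defects may act on liver and muscle separately. Its mouse clamps showed both lower glucose production and higher utilization in VLCAD-deficient animals. The contrast between groups can therefore differ between the two measures, and the plan gives no basis for carrying a power figure from one to the other.

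**Working it through.** **1. Reproduce the stated GIR power.** Inputs from Table 5: SD 9.3 (glycerol) and 7.8 (intralipid); change 31.5 in controls and 5.7 in long-chain patients, so the contrast is 31.5 − 5.7 = 25.8. Sidedness is not stated; two-sided is assumed.

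- SD of change = √(9.3² + 7.8² − 2r·9.3·7.8); at r = 0 this is 12.14.
- SD of the patient-minus-control difference = 12.14·√(2(1 − r_p)); at r_p = 0 this is 17.17.
- Noncentral t, paired, n = 10 (9 df): power 98.8%, against about 97% stated. With 9 pairs it is 97.5%.
- The same method at n = 10 gives 62.6% and 78.1% for PDK4, against 63% and 78% stated, which supports the formula.

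So the 97% is close to what the GIR inputs give, and it uses nothing but GIR inputs. Study Population plans 8 patients per diagnosis, where GIR power at 0.05 is 95.2%.

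**2. Look for Rd inputs.** The documents give no mean, SD or expected difference for Rd. Its power cannot be computed, only bracketed by assumption (step 4).

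**3. False-positive chance under the stated rule.** Setting: no true difference in any group, three long-chain groups, 8 pairs each, paired t, unadjusted 0.05 per comparison. Outcomes within a group are given a common correlation (assumption).

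| Outcomes that could carry the claim | At least one false positive |
|---|---|
| One outcome, unadjusted | 1 − 0.95³ = 14.3% |
| Rd and GIR, either direction | 27% at correlation 0 (1 − 0.95⁶ = 26.5%); 20% at 0.9 |
| Ten insulin-action outcomes, favourable direction only | 53% at correlation 0 (1 − 0.975³⁰ = 53.2%); 47% at 0.3; about 37% at 0.6 |
| One primary outcome, Holm over three groups | about 5% (1 − (1 − 0.05/3)³ = 4.9%) |

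The ten are Rd, GIR, three muscle signalling proteins, two adipose signalling proteins, and three explant uptakes (muscle glucose, adipose glucose, adipose fatty acid). The correlated cases were simulated.

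**4. Power cost of Holm.** 8 pairs, 7 df, level 0.05/3 (Holm's first step). The pair-difference SD is 17.17 with both correlations 0, and 12.91 with both 0.25.

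| Contrast | Correlations 0 / 0 | Correlations 0.25 / 0.25 |
|---|---|---|
| GIR, 25.8 | 83% | 98% |
| Rd, 5 units smaller (20.8), GIR SD: assumption | 63% | 88% |
| Rd, 10 units smaller (15.8), GIR SD: assumption | 38% | 64% |

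**The case against.** **The lack of adjustment is disclosed and reasoned, and some adjustment is offered.** This is true. The plan admits that it cannot power for multiplicity, shows Holm p-values for each outcome, and reserves the MCAD comparison for interval estimation. But Holm works only across disease groups within an outcome, is written for two comparisons where there are three long-chain groups, and is not said to govern the conclusion.

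**A reader might infer that the GIR figures contradict the plan's reason for not adjusting.** They do not. The reason covers every outcome, and PDK4 on Table 5 inputs (contrast 0.62 − 0.18 = 0.44) has only 29% power at zero correlation, or 42% at 0.25/0.25, with 8 pairs at level 0.05/3. Nor can GIR power show that a protected Rd test is affordable. On the assumed Rd contrasts above, the plan's caution looks fair.

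**A reader might also count every planned outcome in both directions and quote a much higher error rate.** The documents do not support that as a measure of this harm. Ectopic lipid is predicted to rise in patients and controls alike, and respiratory quotient is expected to reflect oxidation capacity, so neither tests protection. Only one direction supports the claim.

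**GIR is called a primary result.** The phrase describes what the clamp yields. It does not name a trial endpoint, and neither the hypothesis nor the model is stated in GIR.

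**The Rd figures are chosen, and 7 df may be pessimistic** if the mixed model pools variance across diagnoses. Both points stand. The figures show what Holm could cost and are not an estimate of Rd power.

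**Conclusion.** The point holds in this form: in the text available, Aim 1 has no designated primary outcome, its only power calculation is for a quantity outside its stated outcomes, and the testing rule leaves the protection claim open to several measures. The false-positive chance is about 20% to 27% if only Rd and GIR compete, and about 37% to 53% if ten insulin-action outcomes do, against about 5% with one primary outcome and Holm. These figures assume 8 pairs per group, paired t-tests, equal correlation between outcomes and no true effect; the higher range depends on which outcomes are counted.

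It would go too far to say that the 97% is mislabelled, since the plan states that it is for GIR, or that the trial is underpowered for Rd, which the documents do not allow anyone to calculate. Part of the document was not available, so a designation there cannot be excluded.

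**What to change.** In V. Statistical Analysis:

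1. Name the between-infusion difference in Rd as the single primary outcome of Aim 1. If the sponsor prefers GIR, restate the Aim 1 hypothesis and the model in GIR.
2. Take the confirmatory Aim 1 result from the Holm-adjusted p-values across the three long-chain groups, and correct the count from two comparisons to three.
3. Label all other outcomes secondary or supportive, with unadjusted p-values read in that light.
4. In Power Considerations, state that the Aim 1 power is for GIR only and that none has been computed for Rd. If Rd is chosen, supply a sourced SD and expected difference and compute power at 8 pairs.

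This needs no added patients, visits or assays. The cost is that the other outcomes lose confirmatory status, and that power at the Holm level is below the unadjusted figure: for GIR at 8 pairs and zero correlation it falls from 95% to 83% at Holm's first step, and for Rd it could be well below that.
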